
## **5.0 STUDY POPULATION**

### **5.1 Number of Sites and Subjects**

Approximately 560 men being treated in either methadone maintenance or outpatient drug free treatment will be enrolled into the study (approximately 280 from each modality). Entry into the study is open to adult men of all racial and ethnic groups. Each of the participating CTPs will enroll approximately 40-48 patients. Each clinic's Institutional Review Board will approve recruitment and informed consent procedure. Methadone maintenance clinics will recruit participants who have been enrolled in the clinic for at least 30 days. This will allow time for potential participants to have achieved a stable dose of methadone. For outpatient drug free treatment clinics, efforts should be made to recruit participants immediately upon enrollment in the clinic. This recruitment method will ideally decrease the probability of early drop-out at both types of clinics.

The study will be carried out at a maximum of 7 MMTPs and 7 ODFs, which can each provide approximately 40 men who meet criteria for the study, within a recruitment period of approximately 6-12 months. Final site selection will not occur until the protocol has been

certified and will be in accordance with the CTN CTP selection process for protocol involvement. In selecting CTPs there will be a concerted effort to select clinics that will provide a diverse subject population in terms of ethnic backgrounds, regions of the country and primary drug of abuse. Participants will be recruited through a number of vehicles, as appropriate at each site. Recruitment may include posters and fliers conspicuously placed in CTP waiting rooms, announcements about the study to clinic patients, and directly through a participant's individual counselor.

## **5.2 Duration of Study and Visit Schedule**

Once the protocol has been certified in accordance with the CTN protocol development process, it is anticipated it will take approximately 3-6 months to enroll sites and prepare them for subject recruitment. Participants will be recruited over a 6-12 month period, approximately. It will take approximately 9 months after final subject enrollment to complete the follow up assessment. Data analyses and dissemination of findings will be completed over the following year. Based on this timetable it will take approximately 33 months to complete the study.

The visit schedule is presented in "Figure 2: Study Flow Chart" on page 8.

## **5.3. Informed Consent**

At both screening and entry into the main intervention trial, study staff will obtain written informed consent for study participation. The staff member and the patient will discuss the basic features described in the informed consent form. These include: voluntary nature of participation and freedom to withdraw without consequences to clinic services received, purpose, procedures, randomization, confidentiality, risks, and benefits. It also notifies the participant that all study interviews and treatment sessions will be audiotaped for supervisory and quality assurance purposes. A copy of the proposed consent forms are provided in the appendix.

## **5.4. Inclusion Criteria**

1. Adult males 18 years of age and older in drug abuse treatment at a participating CTP who self report engaging in unprotected vaginal or anal intercourse during the past 6 months. A decision was made by the protocol development committee to not include engaging in unprotected oral sex as an inclusion criteria, because recently published studies indicate it is now considered a low risk behavior for HIV transmission (Page-Shafer, Osmond, Ball et al., 2002; del Romero, Marincovich, Castilla, et al. 2002).
2. Agreeable to being randomly assigned to attend either a one-session standard HIV education session or to the five session REMAS workshop as their HIV education.
3. Agreeable to completing 2-3 hour assessment battery at baseline, 90 minute assessments at three and six months post intervention, and a shorter battery upon completing the intervention.
4. Be able to speak and understand English.

## **5.5. Exclusion Criteria**

1. Observable, gross mental status impairment – including severe distractibility, incoherence or retardation as measured by the Mini Mental Status Exam (a score less than 25).
2. Having a primary sexual partner who is planning on attempting to get pregnant while the participant would be involved in the trial. This is necessary because attempting to become pregnant is incongruent with the primary outcome measure.
3. Current treatment episode of methadone maintenance is less than 30 days.

## **5.6. Subject Discontinuation Criteria**

Participants are free to withdraw at anytime from the study without cause and without penalty from the CTP at which they are receiving their drug abuse treatment. In addition, participants may be withdrawn if it is deemed further participation is harmful to them

Although we anticipate it will be a rare event, a potential problem would arise if a participant drops out of substance abuse treatment (or is discharged from treatment), but wishes to continue attending the protocol intervention to which he is assigned. Since the intent of the study is to evaluate the interventions conducted within treatment programs these individuals will not be allowed to attend intervention sessions, but will be followed to complete follow up assessments. In addition these individuals will be referred to community resources for HIV prevention information if so desired.

### **5.6.1 Consideration of Early Termination**

The Lead Investigators, the CTP Lead Investigator and clinical care providers of the CTP staff may decide to discontinue a subject's participation if it poses a significant risk to his well being. The possibility of partner dissatisfaction with the participant's involvement in the protocol and consequent disruption of the relationship is the only foreseen consequence.

### **5.6.2. Procedures for Discontinuation**

Participants wishing to discontinue participation voluntarily need only to inform the study staff of their wishes and they will be discontinued. If a subject wishes to withdraw from the study, we will ask if he would be willing to participate in the follow-up assessments to prevent missing data where possible.

For participants whom the clinical or research staff feel further participation in the study is detrimental to them, the node project coordinator or designee for the study will meet with the subject in person or over the phone and discuss the pros and cons of his continuation. If the subject chooses to remain in the study, but the project coordinator feels attendance at the groups is detrimental to the subject, the subject will be withdrawn from the groups, but will be allowed to complete follow up assessments. The project coordinator or a clinical staff person identified by the project coordinator will offer up to three debriefing sessions to discuss the discontinuation. Although the investigators recognize the possibility that a subject may need to be discontinued because the intervention is detrimental to him, we judge this to be a very rare event if it happens at all.

## **5.7 Replacement of Subjects**

Participants who discontinue after randomization will not be replaced and will be included in all statistical analyses according to the intent to treat (ITT) design.

## **6.0 STUDY TREATMENTS**

### **6.1 Study Therapies**

There are two intervention conditions in the proposed study: 1) a five-session HIV prevention, communication skills and sexuality workshop, Real Men Are Safe (REMAS); and 2) a single session standard-of-care HIV/AIDS education, serving as a comparison condition. Male CTP drug treatment counselors who receive approximately 20 hours of training will conduct both interventions. Bartholomew et al., (2000), provided 20 hours of training to staff delivering the TOMen program to patients in drug abuse treatment, and this was considered an adequate dose of training. Both interventions are manual-driven. These two features will make ongoing technology transfer to the CTPs highly likely. Both conditions will consist of groups of 3-8 men. Groups will be run by coleaders who will share responsibility for delivery of the treatment (except when only one counselor is available).

#### **6.1.1. HIV/AIDS Education:**

For this protocol session selected educational material from sessions # 1 & 2 of the REMAS workshop will serve as the standard-of-care HIV/AIDS education (See Table 1). This intervention will consist of one approximately 60-minute group session. Using flipchart visual materials, and informational and resource handout materials, the counselor will conduct an approximately 60 minute session covering: HIV/AIDS definitions, transmission, testing and counseling, treatment, and prevention. Certificates will be distributed at the end of the session. Participants will be paid for their attendance to the treatment groups. Reasonable and non-coercive reimbursement sums will be determined on a site-by-site basis. Men will be paid in cash or vouchers (individual participating CTPs will decide if cash or vouchers are to be used) for attending the standard-of-care HIV/AIDS education intervention. It is recommended that participants are paid only if they attend the majority of the session (40 minutes), although the decision to do this may vary based on local IRBs. Paying participants to attend treatment sessions calls into question the issue of sustainability. In the "real world" patients are not paid to attend sessions. Since the current protocol is research, patient participation is completely voluntary. It is the investigators' experience that it is difficult to get a wide representation of patients at voluntary sessions without monetary incentives. If the intervention proves effective then CTPs could make the interventions a mandated part of treatment thus making incentives unnecessary.

#### **6.1.2. Communication Skills and Sexuality Workshop (REMAS)**

The intervention is a five session, approximately 90-minutes/session workshop delivered by male therapists to groups of all male clients. In addition to lecture material, there is liberal use of role-plays and peer group discussions. There is nearly an equal focus on information giving and skills building. Sessions 1, 2, 4 and 5 are all adapted from the PL, TOMen, and HIV-ED materials. Some of the PL materials were revised to be more relevant to an in-treatment population. Session 3 was developed based on research indicating the combining

of sexual behavior and drug use is common among drug abusers and is associated with high risk HIV transmission behaviors and drug use relapse (Calsyn et al, 1995; Calsyn et al, 1999; Calsyn et al 2000). An outline for the intervention is provided in Table 2. Participants will be paid for their attendance to the treatment groups in cash or vouchers. Reasonable and non-coercive reimbursement sums will be determined on a site-by-site basis. It is recommended that participants are paid only if they attend the majority of the session (60 minutes), although the decision to do this may vary based on local IRBs. In an further effort to minimize attrition, the group interventionists or site coordinators will telephone all participants who miss a group and encourage them to attend the next group. In addition they will troubleshoot with the participant to help overcome any barriers to attendance.

## **Table 1. Standard of care HIV/AIDS education: Intervention outline**

Session activities for the Standard of care HIV/AIDS education borrows from the manual Approaches to HIV/AIDS Education Drug Treatment (HIV-ED) and from the Project Light (PL) manual. Pages from these manuals are identified when the activity originates from one of them. Times provided in the table are estimates of the length of time to complete each section.

### HIV/AIDS Update: Identifying Risks

I. Group Introductions. Goals and Guidelines	5 Minutes
II. HIV/AIDS Update	10 minutes
A. HIV-ED pp. 9-16	
B. Introduce HIV Info MAP, AIDS info MAP, HIV Timeline MAP, Body Fluids MAP	
III. HIV Risky Behaviors, injection practices	5 minutes
A. HIV-ED pp. 40-43	
B. Safe injection practices, stress use of new equipment each time over bleach. Do not practice cleaning	
IV. HIV Risky Behaviors, sexual practices	10 minutes
A. HIV ED pp. 33-37, PL Mod 4-X, p. 18	
V. Condom demonstration	10 minutes
A. HIV ED pp. 42-50.	
VI. Barriers to Condom Use	10 minutes
VII. Healthy options	10 minutes
A. HIV-ED pp. 37-39	

## **Table 2. A Communication and Sexuality Workshop: Real Men Are Safe (REMAS): Intervention outline**

Session activities borrow heavily from TCU-IBR DATAR manuals Time Out for Men (TOMen) and Approaches to HIV/AIDS Education Drug Treatment (HIV-ED), and from the Project Light (PL) manuals. Pages from these manuals are identified when the activity originates from one of them.

### Session 1: HIV/AIDS Update: Identifying Risks

I. Group Introductions. Goals and Guidelines	10 Minutes
A. TOMen pp. 6-7	
B. Use pre-group handouts to shorten time, revise purpose to include HIV prevention, interplay between sexual behavior and drug use	
II. Getting Started	10 Minutes
A. TOMen pp. 3-6	
B. Revise purpose to include HIV prevention, interplay between sexual behavior and drug use	
C. minimize focus on intimacy	
III. HIV Risky Behaviors Exercise,	15 minutes
A. HIV-ED pp. 33-37, 43-50	
Add personal assessment activity	
Safety of behaviors, use PL terminology	

- IV. HIV/AIDS Update 15 minutes
  - A. HIV-ED pp. 9-16
  - B. Introduce HIV Info MAP, AIDS info MAP, HIV Timeline MAP, Body Fluids MAP
- V. HIV Risky Behaviors, injection practices 5 minutes
  - A. HIV-ED pp. 40-43
  - B. Safe injection practices, stress use of new equipment each time over bleach.  
Do not practice cleaning
- VI. HIV Risky Behaviors, sexual practices 15 minutes
  - A. HIV ED pp. 33-37, PL Mod 4-X, p. 18
- VII. Condom demonstration 10 minutes
  - A. HIV ED pp. 42-50.
- VIII. Revisit Risky Behaviors Exercise 10 minutes

#### Session 2: HIV/AIDS Update: Planning Prevention

- I. Welcome, redo introductions 5 minutes
- II. Healthy options 15 minutes
  - A. HIV-ED pp. 37-39
- III. Barriers to Condom Use 10 minutes
- IV. Condom Practice 15 minutes
  - PL, MOD.4-III, p13-17
- V. Personalizing commitment to sexual safety 15 minutes
- V. Identifying Triggers 25 minutes
  - PL, Mod. 2-III, p. 6-8
  - PL, Mod. 3-III, p. 8
- VI. Risk Reduction Problem Solving 20 minutes
  - PL, Mod. 3-IV, p. 9-10

#### Session 3: Sex without drugs. Can it happen? Is it Pleasurable?

- I. Welcome, redo introductions 5 minutes
- II. Experience with combining sex & drugs 40 minutes
  - Enhancements
  - Impairments
- III. Enhancing sex without drugs 25minutes
- IV. Coping with sexual impairment without drugs 20 minutes

#### Session 4: Beyond the pick up line, communicating about sex

- I. Welcome, redo introductions 5 minutes
- II. Challenging Stereotypes 30 Minutes
  - TOMen pp. 7-9
- III. Unwritten rules 10 minutes
  - PL, Mod. 5-III, p. 7-8.
- IV. Responsibility in sexual relationships 15 minutes
  - A. TOMen pp. 129-131
  - B. HIV-ED pp. 70-72
- V. Communicating about Safe Sex I 30 minutes
  - A. Assertive TALK, PL Mod 5-IV, pp. 8-11
  - B. TALK Tools, PL Mod 5-IV, pp. 11-14

Session 5: Communicating about Safe Sex II	
I. Welcome, redo introductions	5 minutes
II. Practice TALK	25 minutes
PL, Mod 5-IV (D-E), pp. 15-20	
III. Turning Around Partner Objections	25 minutes
PL, Mod. 6-II, pp. 7-10	
IV. Creative Negotiation	25 minutes
PL, Mod. 6-II, pp. 11-17	
VI. Closing/Wrap-up	10 minutes

## **6.2 Selection and Training of Therapists**

Therapists will be recruited initially from the counseling staff of the CTP sites. Priority will be given to those with group therapy and HIV prevention education experience. Two therapists will be trained for each site. Should there not be two counselors available or interested in conducting the interventions, the node project coordinator for the study will recruit and hire potential therapists from the community at large. Study counselors will receive approximately 20 hours of training in providing the interventions. The interventions are manual driven. The intervention expert and author of the TOMen and HIV-ED interventions, [name], and the lead investigator will conduct training. In addition, [name], a trainer from PL and member of the Northern New England Node, has joined the Protocol Development team and will consult with the training team.

## **6.3 Administration of Study Therapies**

The control condition intervention will be delivered in a single session of approximately 60 minutes (see table 1). The experimental intervention, REMAS will be delivered in five group sessions of approximately 90 minutes each spread out over three consecutive weeks. The intervention will be manual driven (see table 2).

### **6.3.1. Randomization**

As stated in section 4.0, upon completing the baseline assessment participants admitted to the study will be placed into an open cohort of participants waiting for randomization. The cohort will close once there are 8 men in the cohort or four weeks has passed since the first subject was placed in the cohort, whichever comes first. Groups should contain a minimum of 3 participants. If fewer than 3 are recruited during the four weeks, the cohort will remain open until a third participant is recruited. Once closed the cohort will be randomly assigned to attend either the REMAS intervention or the one session standard educational intervention. Separate block randomization schedules will be developed for each CTP with the assumption that 6 cohorts will eventually be randomized. Thus if recruitment is brisk a CTP may end up overshooting their target of 40 participants and actually recruit up to 48 participants. If a CTP has not recruited 40 subjects after six cohorts have been randomized the following procedures will be implemented. If there are less than 29 participants recruited (thus groups are averaging less than 5 participants each) a new block randomization schedule for four cohorts independent from the block randomization for the initial six cohorts will be prepared.

Assuming recruitment rates do not change dramatically the CTP should end up recruiting between 40-48 participants. If between 29-35 participants have been recruited a new block randomization schedule for two cohorts independent from the block randomization for the initial six cohorts will be prepared. If 35 or more participants have been recruited the CTP will recruit one additional cohort which will be randomly assigned to one of the conditions independent of previous cohort assignments in that CTP. The above randomization scheme was chosen over randomizing individuals so that the time participants would need to wait before being provided the intervention would be a maximum of 4 weeks after baseline assessment. With randomizing individuals an extended period of time might pass before enough participants to conduct the intervention had been randomized to one of the conditions.

Randomization will be managed through an outside independent randomization service provided by the Perry Point Cooperative Studies Coordinating Center (PPCSPCC). The PPCSPCC has designed and developed a centralized, automated telephone system to randomize subjects into clinical trials. Study sites access the system using a pre-specified phone number and respond to a series of prompts regarding the subjects' eligibility. After the system verifies subject eligibility, it assigns each subject a treatment assignment. Randomizations can be done 24 hours a day, 7 days a week. Following each randomization, a fax notification is automatically sent to the site and others as needed. The system has also been programmed to send summary reports on a weekly basis.

This methodology does allow for the intervention groups to become slightly unbalanced during the trial within a CTP. With this methodology the group assignments may become predictable toward the end of recruitment to individuals familiar with the randomization scheme. This predictability could threaten the integrity of the randomization if potential participants could manipulate which condition they ended up in by when they enrolled in the study. We will minimize this potential problem by not informing participants of the total number being recruited, thus they will not know when recruiting is near its end when group assignment might be predictable if they knew the number of participants already recruited and to which conditions previous cohorts had been assigned. Another concern with predictability of assignment is with the research assistants as they are conducting initial baseline assessments. The research assistants will be instructed to not speculate/predict with the participants which condition a participant is likely to be assigned to prevent participant bias. In addition the research assistants will be kept blind to the blocked nature of the randomization. Thus from their perspective each cohort's randomization should be independent from previous condition assignments. Since the primary outcome measure is going to be obtained by the ACASI method, it is unlikely any bias the research assistant might have related to predictability of condition assignment would affect the collection of this crucial data.

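### Blocked cohort allocation lets anyone who knows the scheme be certain of about a quarter of assignments while the cohort is still filling, and the concealment of the blocking stops at research assistants

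*Protocol*

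**What the plan says.** Section 6.3.1 fills an open cohort with men who have completed baseline, closes it at 8 men or after four weeks, and only then allocates it: "Once closed the cohort will be randomly assigned to attend either the REMAS intervention or the one session standard educational intervention". The schedule is set clinic by clinic: "Separate block randomization schedules will be developed for each CTP with the assumption that 6 cohorts will eventually be randomized".

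If a clinic is short of 40 men after six cohorts, there are three top-up branches. With fewer than 29 men, a fresh four-cohort schedule is drawn up. With 29-35 men, "a new block randomization schedule for two cohorts independent from the block randomization for the initial six cohorts will be prepared". With 35 or more, one further cohort is allocated independently of what went before.

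The site learns each result at once: "Following each randomization, a fax notification is automatically sent to the site and others as needed". Section 6.3.2 states that neither participants nor therapists can be blinded.

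Section 6.3.1 acknowledges late predictability: "With this methodology the group assignments may become predictable toward the end of recruitment to individuals familiar with the randomization scheme". It lists four safeguards:
- For participants: "We will minimize this potential problem by not informing participants of the total number being recruited".
- Research assistants are told not to predict assignments with participants.
- Research assistants are kept blind to the blocking.
- ACASI is relied on to protect collection of the primary outcome.

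On who recruits, section 5.1 allows "announcements about the study to clinic patients, and directly through a participant's individual counselor". On who delivers the groups, section 6.2 says "Therapists will be recruited initially from the counseling staff of the CTP sites".

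**The concern.** A cohort is filled before it is randomized. If someone at the clinic can already infer its arm, the arm can influence who is put into it. Three features of the plan make that possible. Earlier arms are known at the site by fax and because the trial is open. The schedule lengths are printed in the protocol. The counselors through whom men may be recruited belong to the staff from which the therapists are first drawn. Figure 2 places baseline anywhere from day 1 to day 30, which leaves some room to move a man to an earlier or later cohort.

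Set against this, each safeguard has a limited reach. Withholding the total acts on participants. The instruction not to speculate is meant to prevent participant bias. ACASI protects measurement, not enrolment. Blindness to the blocking is a real safeguard against selection, but it is stated only for research assistants. Nothing comparable covers counselors, therapists or site coordinators.

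At stake is a baseline difference between arms in features such as motivation. The model in section 11.6 adjusts for baseline count, non-monogamy and years of stimulant use, which would remove only part of it.

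**Working it through.** **Inputs.** From section 6.3.1: six cohorts per initial schedule, top-ups of four, two or one, at most 8 men per cohort. From section 11.3: planned effect 0.29 SD, intracluster correlation 0.01, cohort size 8, 200 men per condition required; the planned enrolment of 560 gives 280 per condition. **Assumptions:** each schedule is a single 1:1 block (the ratio is not stated), and the observer knows the scheme and the clinic's earlier assignments.

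**The plan's own figure.** 6 cohorts x 8 men = 48, the stated maximum from the initial schedule. It reproduces.

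**Certain assignments.** There are 20 balanced orders of six cohorts. The next arm is certain once one arm is used up.
- Cohort 4: the first three share an arm in 2 of 20 orders, 0.10.
- Cohort 5: one arm is used up after four cohorts in 8 of 20 orders, 0.40.
- Cohort 6: always, 1.00.

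The sum is 1.5 of 6, or 25%. This agrees with the general formula 2m/(m+1) for a block of 2m: with m = 3, 6/4 = 1.5. Over 14 clinics it is 14 x 1.5 = 21 of 84 cohorts. Cohorts 5 and 6 account for 1.4 of the 1.5 (93%). Always guessing the arm with more places left is right for 4.1 of 6 cohorts, 68%.

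**With top-ups.** A block of four adds 4/3 = 1.33 certain cohorts, a block of two adds 1, and the independent cohort adds none.

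| Clinic pattern | Certain cohorts | Share |
|---|---|---|
| 6 only | 1.5 of 6 | 25% |
| 6 + 4 | 2.83 of 10 | 28% |
| 6 + 2 | 2.5 of 8 | 31% |
| 6 + 1 independent | 1.5 of 7 | 21% |

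If the six were in fact built from smaller blocks, the share would be higher: 39% for 4+2 and 50% for 2+2+2.

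**Illustrated bias.** Suppose men in certain REMAS cohorts are shifted by s SD in one direction and men in certain control cohorts by s SD in the other, unadjusted. Then bias = 2 x s x 0.25 x (share of clinics steering). The design effect is 1 + 7 x 0.01 = 1.07, and SE = sqrt(2 x 1.07/n), which is 0.103 for n = 200 and 0.087 for n = 280 per arm. Type I error = P(|Z + bias/SE| > 1.96).

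| s | Clinics steering | Bias (SD) | Share of 0.29 | Type I error, n = 200 to 280 |
|---|---|---|---|---|
| 0.1 | all | 0.050 | 17% | 7.7% to 8.8% |
| 0.1 | half | 0.025 | 9% | 5.7% to 5.9% |

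**Would varying blocks help?** Take one continuous list per clinic with blocks of 4, 6 or 8 in random order, each size equally likely, and an observer who knows those sizes. Over the first six cohorts:

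| | Fixed six | Random 4/6/8 |
|---|---|---|
| Certain | 25% | 1% |
| Predictable at 75% or better | 32% | 33% |
| Best guess correct | 68% | 65% |
| Clinics 4:2 after six cohorts | 0% | 27% |

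The mean within-clinic information falls to 0.97 of that under exact balance.

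**The case against.** The authors saw the risk, used an independent central service, explained why cohorts rather than individuals are allocated, and listed mitigations. Much of this stands.

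- A reader might infer that the safeguards ignore selection by staff altogether. The protocol does not support that. Research assistants conduct the baseline assessments after which men enter a cohort, and they are kept blind to the blocking. Counselor referral is only one route that recruitment may use, beside posters, fliers and announcements.
- A reader might infer that assignments are foreseeable throughout recruitment. For the initial block the protocol's own description of late predictability is fair: cohort 4 is certain only one time in ten.
- A reader might infer that every top-up raises the share. The branch for 35 or more men lowers it to 21%, and a clinic that reaches 40 men within six cohorts has no top-up.
- A reader might push the illustration further: at s = 0.2 in all certain cohorts at all clinics the type I error would be 16% to 21%. That rests wholly on assumed uniform, two-way steering at every clinic, before covariate adjustment. No figure in the protocol supports any shift, and closing cohorts at 8 men or four weeks limits how long a man can be held back.

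What this does not answer is the gap for counselors, therapists and site coordinators. Section 6.3.1 discusses only participants choosing when to enrol and research assistants at baseline; no stated measure keeps the block structure from other clinic staff.

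**Conclusion.** The concern holds as a gap in allocation concealment. Under 1:1 blocks, 25% of assignments in the initial schedule (21% to 31% per clinic with top-ups) are certain, before the cohort closes, to someone who knows both the scheme and the earlier results. Staff outside the research-assistant role can be in that position and may influence enrolment. The 1:1 single block is inferred, though the protocol's remark on late predictability fits it. The protocol gives no evidence that steering will occur and no basis for its size, so the bias and type I error figures are illustrations, not estimates. The point merits correction because selection of this kind cannot be reliably repaired in analysis and the remedy is cheap.

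**What to change.** State in section 6.3.1 that no clinic staff, including counselors, therapists and site coordinators, know the block structure. Move the block lengths and top-up block rules out of the protocol that sites hold into a restricted document at the central randomization service. In doing so, resolve the overlap at exactly 35 men, which falls under two of the top-up rules. The cost is a wording change and a restricted document; no added visits, staff or participants, and cohort allocation with its four-week rationale is untouched.

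Optionally, have the service run top-ups on down one continuous concealed list per clinic with varying block sizes. This all but removes certain assignments, but it barely lowers best-guess accuracy, does not reduce the share predictable at 75% or better, and leaves about 27% of clinics at 4:2 after six cohorts, for roughly a 3% loss of within-clinic information. Concealment is the main gain; varying the blocks is a supplement to it.
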